10. EFFICACY

Overview

All efficacy variables are initially captured on a continuous or semi-continuous scale. Observed values at the time of collection and change from baseline value at each time point will be summarized descriptively. Mixed Model Repeated Measures (MMRM) analysis will be carried out on change from baseline scores for the primary and secondary efficacy variables for reproxalap-treated subjects (not vehicle-treated subjects). Hereinafter, in this Statistical Analysis Plan, drug-treated shall mean reproxalap-treated. Additional analyses in drug-treated subjects will be performed on certain efficacy variables. Further details of the tests to be performed on each endpoint are given in Table 10.2.1 below. The specific additional analyses are described below.

- 1) The VIIS outcomes will be converted to a binary response variable (yes/no) defined as a 1-unit and 2-unit improvement from baseline. The probability of response in drug-treated subjects will be analyzed over time using generalized estimating equation (GEE) models.
- 2) Change from baseline over time will be converted into an Area Under the Curve (AUC) value using the trapezoidal rule. AUC for drug-treated subjects will be inferentially compared to zero (0 = no change from baseline) using a linear model.
- 3) Time to first response (1-unit improvement and 2-unit improvement) for the VIIS outcomes (scaling and erythema) will be evaluated using a Kaplan Meier survival curve for drug-treated subjects.

Tables will be generated for each endpoint presenting appropriate descriptive and inferential statistics to convey the results of the analyses. Tables will be augmented by figures for selected analyses.

10.1. PRIMARY EFFICACY ENDPOINT AND ANALYSIS

The primary endpoint for the clinical trial is change from baseline in the VIIS scaling score in drug-treated subjects, as assessed by the investigator, in the target efficacy area. The VIIS provides five-point Likert scales (range 0-4) for erythema and scaling that increases in severity with increasing score values.

The target efficacy area for all efficacy analyses will be one of the body sites as defined in the VIIS tool (with the exception of Dorsal foot) with Grade 2 or higher on baseline VIIS scaling score as assessed by the Investigator.

The within-group change from baseline will be the primary focus of interest in the primary analysis.

Syneos Health #1009367

Primary Analysis

A Mixed Model Repeated Measures (MMRM) model will be used to perform the primary analysis of the VIIS scaling score in drug-treated subjects (not vehicle-treated subjects). Change from baseline VIIS scaling score will serve as the dependent variable. The model will include the baseline value (Visit 1) as a covariate (if useful) and visit (treated as a factor; the visit term will cover Visit 1, 5, 7, and 8). An unstructured covariance structure will be assumed and a Type III model will be evaluated. If the unstructured covariance structure matrix results in a lack of convergence, then Toeplitz (TOEP), first-order autoregressive (AR1), compound symmetric (CS) covariance structure will be used in that order. If the MMRM model cannot hit convergence with any correlation structure, then a within-subject t-test (baseline-adjusted, if useful) will be used to compare baseline to Visit 8. It should be noted that improvement will be signified by the existence of a negative change score.

The primary efficacy endpoint will be summarized descriptively by visit and across all visits. The table will contain descriptive statistics on observed values and change from baseline at each time point.

The primary analysis using the MMRM model will be summarized in a consolidated table containing the following:

- Descriptive statistics for change scores at baseline and each post-treatment time point.
- The LS mean change scores with accompanying standard errors and 95% confidence intervals for each visit.
- Within-group contrasts for each given visit.
- Significance levels for the visit effects.

Along with the table detailing the results of the MMRM model, a consolidated table presenting the essential information for the primary analysis will be constructed. The primary endpoint will be deemed to have been met if the Visit 8 (week 24) term is significant, and the term coefficient is negative.

Secondary and Sensitivity Analyses Related to the Primary Outcome Variable

The following analyses will be performed to provide additional insight into VIIS scaling.

Responder Analysis

For drug-treated subjects, responder status will be assigned to a subject if at a given post treatment time point an improved change from baseline of at least 1 VIIS scaling

Syneos Health #1009367

unit occurs. A Generalized Estimating Equation (GEE) model will be used to evaluate the predicted log odds, odds and probability of response. The model will include the effect of visit (treated as a factor). An unstructured covariance structure will be assumed and a Type III model will be evaluated. If the unstructured covariance structure matrix results in a lack of convergence, then first-order autoregressive (AR1) and compound symmetric (CS) covariance structure will be used in that order.

Results will be captured in a consolidated table that contains the following information:

- Number and percent of observed responders and non-responders at all post-treatment time points;
- Significance levels for the visit effects;
- The model predicted log odds, odds and probability of response with standard errors and 95% confidence intervals for each visit;
- Within-group contrasts expressed as an odds ratio, accompanied by a 95% confidence interval.

AUC Analysis

For drug-treated subjects, AUC for change from baseline over all post-treatment time points will be calculated for each subject using the trapezoidal rule. A linear model comparing AUC to zero (no change from baseline) will be performed.

Survival Analysis

For drug-treated subjects, time to first response (i.e., a one-unit VIIS scaling improvement) will be captured in a Kaplan Meier plot. A hazard rate estimate will be generated.

Analysis for Patients Experiencing one or more Treatment interruptions

The impact of Treatment interruptions on the primary outcome will be evaluated through sensitivity analysis. Patients with a treatment interruption of more than 1 week will be flagged. The same MMRM model of the primary analysis will be conducted on the ITT population with the treatment interruption as a categorical variable and the treatment interruption by treatment interaction as an additional independent variable. The analysis outcome will be summarized in the similar way as the primary analysis. Estimates of the treatment interruption effect variable will also be tabulated.

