5.3. DETERMINATION OF SAMPLE SIZE

Part 1 of the clinical trial will assess the effect size on the VIIS scaling score with ADX-102 1% topical dermal cream, and will confirm the sample size needed for Part 2. Unblinded Part 1 safety and efficacy results will be available to the Sponsor for administrative consideration and use upon completion of Part 1. Efficacy data will be used to confirm the sample size estimation for Part 2 as well as to perform between groups and within group descriptive and inferential statistical analyses

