8. GENERAL ASPECTS FOR STATISTICAL ANALYSIS

8.1. GENERAL METHODS

All patients entered into the database will be included in patient data listings. Summary tables will be provided for all patients.

Unless otherwise specified, all demographic, baseline and safety data will be presented by treatment arm and overall. Efficacy data will be presented by treatment arm.

Quantitative (continuous) data - absolute values and changes from baseline, where appropriate - will be summarized with number of observations (n), mean, standard deviation (SD), median, minimum, and maximum and 1st and 3rd quartiles for efficacy tables only.

Qualitative (categorical) data will be summarized using number of observations (n), and frequency and percentages of patients. Unless stated otherwise, the calculation of percentages will be based on the total number of patients with non-missing data in the set of interest.

Comparisons will contrast outcomes between time points within both ADX-102 1% and Vehicle treatment groups as well as contrast outcomes between each of these treatment groups.

- All primary and secondary efficacy analyses will be performed on the m-ITT population.
- The safety analysis will be performed on the SAF population.

Summary tables will include outcomes for a given treatment at a given time point, the between group differences in change from baseline at each time point, and the within group difference at each time point.

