8.3. DATA CONSIDERATIONS

Due to the limited sample size for Part 1 of the clinical trial, descriptive statistics are planned for the primary and secondary endpoints. Inferential statistics will be used for the primary analysis.

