10.2. SECONDARY EFFICACY ENDPOINTS AND ANALYSES

Change from baseline will be calculated for all secondary efficacy variables, namely:

Syneos Health #1009367

VIIS Scores:

- VIIS erythema score
- Central reader assessed VIIS scaling and erythema scores
 - Clinical Outcomes Assessments
- The EQ 5D 5L patient/caregiver overall assessment score
- The clinical global impression of severity scale, the patient/observer global impression scales
- The patient-/observer-reported scratching scales,
- The patient-/observer-reported burden of bathing/showering, the patient reported itching scale,
- The CDLQI/DLQI scales,
- Lipid biomarker measurements and TEWL (exploratory biomarkers).

[figure not shown]
It will be noted that in addition to an overall Visual Analog Scale (0 to 100) assessment that measures self-reported health, the EQ-5D-5L also evaluates, by category (no problem, slight problems, moderate problems, severe problems and extreme problems), the status of a subject in five domains (Mobility, Self-Care, Usual Activities, Pain/Discomfort and Anxiety/Depression). Guidance documentation for the use of the EQ-5D-5L specifically warns against the conceptualization of these categories as a mathematically meaningful 5-point scale, thus only the VAS scale (not individual domain categorical results) will be statistically evaluated.

The secondary efficacy variables are given in section 6, with further detail of each score given in Table 10.2.1 below. The schedule of assessments is given in Section 4 and each individual score is shown in Appendix 1-Outcome Scales.

[figure not shown]
Table 10.2.1: Description of secondary efficacy variables

Syneos Health #1009367

Syneos Health #1009367

Secondary Analysis

The secondary efficacy variables will be analyzed using one or more of the following analyses applied to the primary endpoint:

1. A MMRM generalized linear model applied to secondary efficacy variable change scores derived from observed values;

Syneos Health #1009367

- 2. A GEE model applied to secondary efficacy variable scales after dichotomization to reflect response (yes/no);
- 3. A linear model applied to secondary efficacy variable observed values after transformation to an AUC measurement;
- 4. A log rank analysis and a proportional hazards model applied to time to first response.

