10.4. EXPLORATORY ANALYSES

Efficacy Endpoint

Additional exploratory analysis maybe conducted on primary efficacy endpoint by sponsor. Exploratory analysis will be conducted for both targeted efficacy area and for combined regions as appropriate, such as but not limit to:

- 1) Repeat primary analysis MMRM model on drug-treatment patients to evaluate change from baseline for combined visits (Visit 5, Visit 7 and Visit 8)
- 2) Repeat primary analysis MMRM model on all treated patients (including both drug-treatment and vehicle-treated patients) to evaluate change from baseline for combined visits (Visit 5, Visit 7 and Visit 8) and each individual visit
- 3) all patients (including both drug-treatment and vehicle treated patients)
- 4) Responder analysis for patient with at least 2 units VIIS scaling improvement from baseline at any post treatment time point
- 5) Survival analysis for the time to first response defined as 2 units VIIS scaling improvement from baseline
- 6) AUC analysis for change from baseline of all VIIS regions combined
- Analyze change from baseline of VIIS total score at week 24 analysis using MMRM model
- 8) Contralateral analysis of between group contrast comparing VIIS scaling score change from baseline between treated area vs. untreated area
- 9) To further evaluate the impact of 'treatment interruption' on treatment effect, the same analysis approach used for primary analysis on primary endpoint may be repeated on following subgroups:
 - a. patient with 'treatment interruption' for at least 1 week

Syneos Health #1009367

b. patient without 'treatment interruption' or with 'treatment interruption' for less than 1 week

Biomarker Endpoint

Selected skin lipid bio markers, captured as the post-treatment value at Week 24 or at an early termination visit as the post-treatment minus baseline value (change score), may be correlated with various outcome symptom scales or functions of outcome symptom scales. Such skin lipid biomarkers are listed in Table 10.3.1.

Exploratory analyses will be performed on lipid biomarkers from skin cell analysis and TEWL using the following methodologies:

Analysis between biomarkers and outcome scales (investigator and central reader VIIS scaling and erythema) for time matched assessments will be performed using appropriate correlation procedures.

Table 10.3.1: Lipid Values Selected for correlational analysis (captured as post treatment values or change score values)

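### The Part 1 interruption analysis in SAP 10.1 cannot be fitted as written, and the between-group inference promised in SAP 5.3 has no fully specified model

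*SAP*

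**What the plan says.** - **Primary model.** The overview of SAP Section 10 plans an MMRM "for the primary and secondary efficacy variables for reproxalap-treated subjects (not vehicle-treated subjects". SAP 10.1 uses it to "perform the primary analysis of the VIIS scaling score in drug-treated subjects (not vehicle-treated subjects", with a visit factor and, if useful, baseline; there is no treatment term. The endpoint is "deemed to have been met if the Visit 8 (week 24) term is significant, and the term coefficient is negative".
- **Interruption analysis.** Under treatment interruptions, SAP 10.1 reruns the same MMRM on the ITT population, adding an interruption factor and its interaction with treatment. SAP Section 7 defines an m-ITT population but no ITT population.
- **Between-group promises.** SAP 5.3 says Part 1 efficacy data will be used to "perform between groups and within group descriptive and inferential statistical analyses". SAP 8.1 says summary tables will include "the between group differences in change from baseline at each time point". SAP 8.3 plans descriptive statistics for primary and secondary endpoints, then adds: "Inferential statistics will be used for the primary analysis".
- **What Section 10 offers on vehicle.** SAP 10.2 lists, for secondary variables, "A log rank analysis and a proportional hazards model applied to time to first response", without naming groups. SAP 10.4 lists, among analyses the sponsor may choose to run, "Repeat primary analysis MMRM model on all treated patients (including both drug-treatment and vehicle-treated patients", without naming a treatment term or contrast.
- **Protocol.** Protocol 10.4 planned an MMRM with treatment, time and treatment x time, and active-minus-vehicle contrasts at each time point. SAP Section 2 says the SAP supersedes the protocol's methods. SAP Section 13 lists only visit windows as a change.

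**The concern.** The interruption analysis asks for a term that its own model cannot hold. SAP 8.6 and 9.2.1 record that a subset of subjects had interruptions, so this analysis will be needed and the programmer would have to guess what was meant.

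The inferential between-group analysis in SAP 5.3 is promised but not specified. Whether and how drug is modelled against vehicle would then be settled after Part 1 is unblinded.

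This matters although Part 1 carries no efficacy claim. Under Protocol Section 10, one condition for starting Part 2 is a mean change in the active arm near or above 0.5 units. SAP 10.2 defends the within-arm view on the ground that SLS symptoms do not improve spontaneously. That answers natural history. It does not answer the effect of the vehicle cream, or of emollients, which Protocol 5.7.2.1 allows on treated skin. Vehicle subjects are randomised and rated on the same schedule, so the data for a comparison will exist.

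**Working it through.** **1. The plan's own figure.** Protocol 10.1 sizes Part 2 with a two-sided one-sample t-test: n = 20, change 0.5, alpha 0.05. With noncentrality 0.5/SD x sqrt(20), power is 94.2% at SD 0.6 (stated 94%) and 85.8% at SD 0.7 (stated 85%). Both reproduce. The documents state no power for Part 1.

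**2. Interruption model, drug arm only.** Take the columns intercept, interruption, treatment, interruption x treatment.
- Every subject is on drug, so treatment = 1 = intercept.
- Hence interruption x treatment = interruption.
- Rank is 2 of 4. Adding visit columns does not help: intercept, two visit columns, interruption and interaction make 5 columns with rank 4.

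The interaction duplicates the interruption main effect and has no estimate of its own.

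**3. Interruption model, both arms.** Suppose ITT means the protocol's both-arm population (Protocol 10.2: randomised, dosed, any post-dose assessment). The model is then not the same one, no treatment main effect is stated, and the population differs from the SAP's m-ITT (at least one VIIS after Visit 2). With 6 drug and 3 vehicle subjects (protocol synopsis), a treatment main effect, and both kinds of subject in the drug arm:

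| Vehicle subjects interrupted | Rank (of 4) | Interaction estimable |
|---|---|---|
| 0 of 3 | 3 | no |
| 1 or 2 of 3 | 4 | yes |
| 3 of 3 | 3 | no |

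**4. Promise against specification.**

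| Place | Between-arm content | Model given |
|---|---|---|
| SAP 5.3 | inferential and descriptive | none |
| SAP 8.1 | differences at each time point | none; can be met descriptively |
| SAP 10.1 | none; drug arm only | not applicable |
| SAP 10.2, item 4 | log-rank and proportional hazards | no groups named; to mirror 10.1, whose survival analysis is a drug-only Kaplan-Meier plot |
| SAP 10.4, item 2 | MMRM on both arms | optional; repeats a model without a treatment term |
| Protocol 10.4 | treatment, time, treatment x time | yes, but absent from the SAP and from its Section 13 |

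A log-rank test needs at least two groups. Pooling both arms in a model without a treatment term gives an average over arms, not a drug effect.

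**5. What a drug-versus-vehicle estimate would deliver at 6 v 3.** SDs of 0.52, 0.6 and 0.7 come from Protocol 10.1 and are assumed equal in both arms, with no dropout and a t-test in place of the MMRM.
- Half-width = t(0.975, 7 df) x SD x sqrt(1/6 + 1/3) = 2.365 x 0.6 x 0.707 = 1.00 grade (0.87 at SD 0.52; 1.17 at SD 0.7).
- Power for a difference of 0.5, noncentrality 0.5/(0.6 x 0.707) = 1.18: 17.6% (21.8% at SD 0.52; 14.2% at SD 0.7).

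This is an estimate to read beside the drug-arm result, not a test.

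**6. Illustration of what the drug-only rule cannot see.** The documents give no vehicle mean, so the non-drug change is assumed. The one-sample t-test at n = 6 (two-sided 0.05, negative direction) is close to the SAP's fallback test. With no true drug effect:

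| Assumed non-drug change | SD 0.52 | SD 0.6 | SD 0.7 |
|---|---|---|---|
| -0.2 | 12% | 10% | 8% |
| -0.3 | 21% | 17% | 14% |
| -0.5 | 48% | 38% | 30% |

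The nominal rate in that direction, with no change at all, is 2.5%.

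**The case against.** The case for leaving the plan alone is substantial.

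- **The within-arm focus is open and reasoned.** SAP 8.2, 10.1 and 10.2 state it, and Protocol 10.1 sizes the trial on it. The protocol synopsis and Section 10 let Part 1 analyses be confined to description because of the 6 and 3 subjects, and SAP 8.3 largely does so. Protocol 10.4 does not expect between-group significance. This stands. It leaves the inference promised in SAP 5.3 and the missing Section 13 entry, and it does not touch the interruption analysis.
- **Vehicle is not ignored.** SAP 8.1 plans between-group differences descriptively, and 10.2 and 10.4 contain the items listed above. Table 10.2.1, to which the SAP refers for test details, is not visible in the public text, and Table 10.2.2 appears to have lost rows. A reader might infer that Section 10 contains no both-arm analysis at all. The documents support only the narrower statement that the visible text gives no fully specified drug-versus-vehicle model.
- **The only vehicle evidence points to little vehicle change.** Protocol 1.3.1 reports that drug was statistically superior to vehicle in the 12-subject Phase 2 study, randomised 1:1. With SD 0.52 and a t-test at 6 v 6, significance needs a difference of about 2.228 x 0.52 x sqrt(2/6) = 0.67. Against the mean change of -0.7 in Protocol 10.1, taken as the drug arm's, that puts vehicle near zero. The test and scale may differ, so this is only a rough bound, but it makes the -0.5 row in step 6 hard to defend.

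Two further inferences are tempting and should not be drawn.

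- **Bias from choosing the worst-scoring site.** The documents do not say which rating selects the site. The VIIS form in SAP 20.2 speaks of a site already selected when the rating is made. Protocol 6.12 uses the VIIS scaling scale in the dermatologic exam, which is also done at Screening. Rater reliability is not given.
- **Bias from omitting the treatment main effect in a two-arm interruption model.** This depends on coding. With class variables the design keeps rank 4 and the interaction term simply absorbs treatment.

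**Conclusion.** The point holds in two parts and should be fixed before Part 1 is unblinded.

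The interruption analysis is wrong as written. This follows from the design alone and needs no assumption about the data. The term is not estimable in the drug arm. With both arms and a treatment main effect it is estimable only if each arm has interrupted and uninterrupted subjects. The named population is undefined in the SAP.

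The between-group part is a gap in specification and documentation. An inferential analysis is promised without a model in the visible text, and a protocol model has gone without an entry in Section 13. Restoring a comparison would give an interval of about plus or minus 1.0 grade at SD 0.6 (0.87 to 1.17 over SD 0.52 to 0.7), assuming equal SDs and 6 v 3 complete. The rates in step 6 are illustrations on assumed values and carry no part of this conclusion.

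A reader might go further and infer that the drug-arm primary analysis is invalid, or that the Part 2 claim is compromised. The documents do not support either. The primary is a disclosed choice. Protocol Section 10 rests the claim on Part 2 only, and the SAP covers Part 1 only, so the protocol's MMRM for Part 2 is untouched.

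**What to change.** - Keep the drug-arm MMRM and its success rule as the primary analysis, unchanged.
- Beside it, add an MMRM on both arms of the m-ITT with baseline, treatment, post-baseline visit and treatment x visit. Report the Week 24 drug-minus-vehicle estimate with its 95% CI, labelled as estimation only.
- Run the interruption analysis in that both-arm model with a treatment main effect. Include the interaction only if both arms contain interrupted and uninterrupted subjects; otherwise fit the interruption main effect only. Replace ITT with m-ITT in that paragraph.
- Align SAP 5.3, 8.1, 8.3 and the log-rank item in 10.2 with this, and list the change from Protocol 10.4 in Section 13.

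The cost is SAP wording and one more model statement, with no new data or visits. The downside is one more result with a very wide interval. The both-arm model should stand beside the drug-arm analysis and not replace it. Pooling the residual variance is safe for the drug-arm interval only if the arms have equal variances: with drug SD 0.6 and vehicle SD 0.3, coverage of the nominal 95% drug-arm interval falls to about 92%.

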8.2. CONTINGENCIES DUE TO LIMITATIONS INHERENT IN SLS RESEARCH

There will be no adjustment for multiplicity in the analyses of primary and secondary endpoints. The limitations of achieving statistical power due to the limited availability of subjects as well as the longevity and consistency of SLS symptoms make statistical significance difficult to achieve.

In this Phase 3 clinical trial, efficacy decisions must rely upon a clearly observable trend in change in skin scaling, a socially stigmatic symptom of great discomfort that absent a novel treatment will require an inordinate amount of attentiveness on a daily basis for the life of the patient. Thus, significance levels are provided in this clinical trial as an additional index of change rather than an inferential expectation.

Syneos Health #1009367

If warranted by observed data characteristics relative to model assumptions, non-parametric methods and small sample statistical methods may be substituted for one or more of the below anticipated model based analyses. The rationale for any such change will be provided.

Finally, if statistical power is materially increased through the addition of one or more continuous or stratification covariates to a statistical model described in this SAP, the model will include the covariate(s). Analogously, if stratification adds power to a non-parametric or small sample procedure, the analysis will include stratification.

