8.4. KEY DEFINITIONS AND TERMINOLOGY

Reference start date and study day

Study Day will be calculated from the reference start date and will be used to show start/stop day of assessments and events.

Baseline Value

For purposes of analysis, the baseline value is defined as the last non-missing value obtained prior to initiation of study drug.

Change from Baseline.

Change from baseline for a given endpoint is defined as the difference between a post-treatment study day value and the baseline variable value and will be calculated directionally as post-study minus baseline.

Note that for the VIIS, it is planned that a single investigator will complete this instrument prior to randomization on day 1 of Part 1.

Day 1 (Baseline)

Day 1 is the earliest day that the study drug is first initiated.

Age

Syneos Health #1009367

Age is calculated as the number of whole years from a subject's date of birth to the date of informed consent.

Study Visit.

Study visit is the nominal visit as recorded on the eCRF.

Total Days on Study

Total days on study is defined as the number of days from Day 1 to the date of completion or early termination.

Last Dose of study drug

Last dose of study drug is defined as the number of days from day 1 to the date of last dose of study drug.

Duration of SLS.

The duration of SLS is defined as the number of whole years from the date of onset of SLS diagnosis to the date of informed consent.

Adverse Event

An adverse event is any untoward medical occurrence in a patient or clinical investigation patient, temporally associated with the use of a medicinal product, whether or not considered related to the medicinal product.

Treatment Period

The Treatment Period covers the duration that a patient is in the study from Baseline (Day 1) to Week 24.

Safety Follow-up Period

The Safety Follow-up Period continues for 28 days after the last dose of study treatment at Week 24 through Week 28.

Definition of Study Completion

A patient will be defined as "completed" if she or he completes the Week 24 study visit.

End of Study Definition

Syneos Health #1009367

End of study is defined as the date when the patient has completed one of the following: completed the follow-up visit after the Week 24 visit, permanently discontinued from the study, or lost to follow-up.

Day of Study Termination

Day of study termination = Termination Date - Date of Baseline (Day 1) + 1.

Percent Change from Baseline

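### SAP 10.1 models change from baseline but lists Visit 1, where every change is 0, as a visit level; if those records are kept and the model falls back to Toeplitz, the Week 24 standard error is distorted

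*SAP*

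**What the plan says.** SAP 10.1 fits the primary MMRM to drug-treated subjects only. On the response it says: "Change from baseline VIIS scaling score will serve as the dependent variable". The factor is "visit (treated as a factor; the visit term will cover Visit 1, 5, 7, and 8", and the Visit 1 value may also enter as a covariate if useful. The covariance is unstructured first. If that does not converge, "then Toeplitz (TOEP), first-order autoregressive (AR1), compound symmetric (CS) covariance structure will be used in that order". Last comes: "If the MMRM model cannot hit convergence with any correlation structure, then a within-subject t-test". The endpoint is met if "the Visit 8 (week 24) term is significant, and the term coefficient is negative".

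Other places bear on Visit 1:

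- SAP 8.4 takes baseline as the last value before study drug, with the VIIS completed on Day 1 before randomization. It also says: "Change from baseline for a given endpoint is defined as the difference between a post-treatment study day value and the baseline variable value".
- SAP 10.4, when it repeats the primary model for combined visits, names only Visits 5, 7 and 8.
- The output list in SAP 10.1 asks for descriptive statistics of change at baseline as well as at each later time point.

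**The concern.** A change score at baseline carries no information, because it is 0 by definition. As a level of the visit factor it gives the covariance matrix a row with no variance. The unstructured model cannot be maximised with such a row. Toeplitz, AR(1) and compound symmetry, as named, each assume one variance for all visits, so they average the artificial zero with the three real visits.

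The success rule then becomes unclear. The tested term could be the Visit 8 LS mean or the Visit 8 coefficient against Visit 1. With complete data and no covariate these are the same number, since the Visit 1 mean is exactly 0, and they should have the same SE. Under Toeplitz with Visit 1 kept they do not.

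At stake are the Part 1 verdict on the primary endpoint and its Week 24 SE, confidence interval and p-value. The treatment-interruption sensitivity analysis (SAP 10.1) and the secondary MMRMs (SAP 10.2) reuse the model.

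**Working it through.** **Inputs.** Drug-treated subjects n = 6 (Protocol synopsis, Statistical Analysis). SD of change 0.6 (Protocol 10.1, taken from planning of Part 2). The documents give no SDs by visit, correlations or degrees-of-freedom method. Assumed here: complete data, no covariate, equal SDs at Visits 5, 7 and 8, exchangeable correlation 0.2 to 0.9.

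**The plan's own figure.** The SAP gives none for this model. The nearest is the one-sample t-test power in Protocol 10.1 (n = 20, change 0.5): 94% at SD 0.6 and 85% at SD 0.7. The noncentral t gives 94.2% and 85.8%. These concern Part 2 and are not affected.

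**Step 1: correct SE.** 0.6/√6 = 0.245. With Visits 5, 7 and 8 only, complete data and no covariate, the unstructured Visit 8 test is the one-sample t-test with 5 df.

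**Step 2: unstructured, Visit 1 kept.** With saturated visit means, −2 REML = (n−1)[log|Σ| + tr(Σ⁻¹S)], constants dropped. The Visit 1 row and column of S are 0. Give Visit 1 variance v and zero covariance, and set the 3×3 block to its sample value S₃. Then −2 REML = 5[ln v + ln|S₃| + 3]. At correlation 0.5, |S₃| = 0.36³ × 0.5² × 2 = 0.0233 and ln|S₃| = −3.758.

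- v = 10⁻²: 5(−4.605 − 3.758 + 3) = −26.8
- v = 10⁻⁴: −49.8
- v = 10⁻⁸: −95.9

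Each factor of 100 lowers it by 5 × ln 100 = 23.0, without limit, so there is no maximum. A program may report failure, or may stop at a tiny v and report convergence. In the second case, without a covariate, the Visit 8 SE is still 0.245. With a baseline covariate (common slope) the Visit 1 zeros drive the slope to 0: in one example it was −0.300 without the Visit 1 records and −0.00000003 with them.

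**Step 3: Toeplitz, Visit 1 kept.** Minimise the same criterion with Σ = σ²R, R Toeplitz. Then SE(LS mean) = √(σ²/6) and SE(Visit 8 − Visit 1) = √(2σ²(1 − r₃)/6), where r₃ is the lag-3 correlation.

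| Correlation | σ² | r₃ | LS-mean SE (ratio to 0.245) | Contrast SE (ratio) |
|---|---|---|---|---|
| 0.2 | 0.2690 | −0.025 | 0.212 (0.86) | 0.303 (1.24) |
| 0.5 | 0.2626 | −0.159 | 0.209 (0.85) | 0.318 (1.30) |
| 0.8 | 0.2529 | −0.401 | 0.205 (0.84) | 0.344 (1.40) |
| 0.9 | 0.2492 | −0.485 | 0.204 (0.83) | 0.351 (1.43) |

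Toeplitz on Visits 5, 7 and 8 alone gives 1.00 in all four rows, so here the whole error comes from Visit 1. A hand check uses compound symmetry, the last covariance fallback: the common variance is (0 + 3 × 0.36)/4 = 0.27, the LS-mean SE is √(0.27/6) = 0.212, and the ratio is √(3/4) = 0.87.

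In simulated normal data with these equal SDs (correlation 0.3 to 0.8), two-sided type I error of the LS-mean test under this fallback was 8.5% to 10.6% with Satterthwaite or 15 df.

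**Step 4: unequal SDs.** Ratios to the true Visit 8 SE, at the highest maximum of the likelihood:

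- SDs 0.3/0.45/0.6: LS mean 0.67 to 0.69, contrast 0.91 to 0.95; Toeplitz without Visit 1 about 0.78.
- SDs 0.9/0.8/0.6: LS mean 1.14 to 1.16, contrast 2.03 to 2.14; Toeplitz without Visit 1 about 1.29.

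The direction can therefore reverse, and part of the error is Toeplitz's common variance. In the second pattern the likelihood has another maximum at correlations 0.2 and 0.5. There the contrast ratio is 1.16 and 1.25 instead of 2.03 and 2.07, and at correlation 0.2 the two maxima differ by only about 0.12 in −2 REML. Contrast figures there are not unique.

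**The case against.** The best defence is that SAP 8.4 and 10.4 already imply Visits 5, 7 and 8, so a sensible programmer would drop Visit 1. That may happen. But 10.1 is the specific text for the primary model, it names Visit 1, and its output list expects a change score at baseline. Two programmers could build different models from this SAP.

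Second, the Toeplitz step is not certain. A reader might infer that the plan must reach it. The documents do not support that: the fallback depends on reported non-convergence, and software may stop at a near-zero variance with the Visit 8 SE intact if there is no covariate. This limits the point, although a correct SE would then depend on how the software behaves.

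Third, SAP 8.2 says "significance levels are provided in this clinical trial as an additional index of change rather than an inferential expectation". Protocol 10 allows Part 1 p-values to be omitted, and the SAP covers Part 1 only. This limits the reach. It does not remove the point, because SAP 8.3 states "Inferential statistics will be used for the primary analysis" and 10.1 sets a rule for declaring the endpoint met.

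Fourth, a reader might conclude that Toeplitz, AR(1) and compound symmetry should give way to the t-test. That is a trade-off, not an error correction: with no imputation (SAP 8.5), the t-test omits subjects without Visit 8, whereas the mixed model uses their earlier visits.

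**Conclusion.** The specification of the primary model is inconsistent and should be corrected. That the unstructured likelihood has no maximum with Visit 1 kept does not depend on the assumed SDs. The distortion of the Visit 8 SE depends on two conditions: the Visit 1 records are kept, and the unstructured fit is reported as failed. Under the equal-SD assumptions, the LS-mean SE is then 14% to 17% too small and the contrast SE 24% to 43% too large.

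Two stronger readings should be resisted. One is that the Part 1 test is known to be too liberal, or too conservative. The direction depends on which quantity is tested, the SDs by visit and the degrees of freedom, none of which the SAP gives. The other is that the trial's efficacy claim is affected. It is not: the claim rests on Part 2 (Protocol 10 and 10.4), and the decision to start Part 2 and its sample size use the mean change and SD, not this SE. With complete data and no covariate, the Week 24 point estimate is also unchanged.

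**What to change.** In SAP 10.1:

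1. Restrict the response records and the visit factor to Visits 5, 7 and 8. Use the Visit 1 value only as the optional covariate, and show observed values, not change, in the baseline row of the output table.
2. Define success as a negative Visit 8 LS mean change with two-sided p < 0.05 against 0, and name a small-sample degrees-of-freedom method. SAP 10.1 states no alpha; 0.05 two-sided is the level in Protocol 10.1. This step is needed even after step 1, because a Visit 8 coefficient against another post-baseline visit would test something else.
3. Carry the same wording into the interruption analysis and the secondary MMRMs.

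This does not guarantee an unstructured fit. With 6 subjects and changes rounded to whole grades, the 3×3 sample covariance was singular in 14% (correlation 0.5) to 34% (correlation 0.8) of simulated trials, and in 6% to 76% over a wider set of assumed SDs. Reporting the within-subject t-test already in the plan beside any Toeplitz, AR(1) or compound-symmetry result is therefore a useful optional check.

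The cost is a few sentences of SAP wording and no new data.
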